variably according to the patient's IMDC (International mRCC Database Consortium) risk score. IMDC represents a large collection of real-world data (RWD) on patients with advanced kidney cancer treated with targeted therapies [7,8]. IMDC combinations available for favourable risk patients include pembrolizumab + axitinib, nivolumab + cabozantinib and pembrolizumab + lenvatinib; for intermediate or poor risk patients the combination of ipilimumab and nivolumab is recommended in addition to the aforementioned three combinations. None of the recommended first-line treatment options have been compared head-to-head but all of the pivotal clinical studies have sunitinib monotherapy as a control, a former standard-of-care (SoC). The current second and later line treatment recommendations include VEGFR-TKI monotherapies, such as pazopanib and sunitinib, but will likely be reshaped in the coming years as clinical evidence on the optimal treatment sequence is accumulated.

The prognostic model constructed by the IMDC has been used to stratify patients in contemporary clinical trials and to provide risk-directed treatment selection in everyday clinical practice. The IMDC prognostic model contains six independent predictors of poor survival, which are: Karnofsky performance status of less than 80%, less than 1 year from diagnosis to treatment, anaemia (haemoglobin concentration <lower limit of normal), hypercalcaemia (corrected calcium concentration >upper limit of normal), neutrophilia (neutrophil count >upper limit of normal), and thrombocytosis (platelet count >upper limit of normal). An IMDC risk score is determined for a patient according to the number of poor prognostic factors the patient has; favourable risk patients have 0 factors; intermediate risk patients have one or two factors; and poor risk patients have three or more factors.

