7.2.3. Patient stratification

Analyses will be stratified by:

- IMDC risk category (defined at the initiation of the first treatment for the metastatic RCC; see Table 1 and listing below for definitions)
 - Applied to all primary and secondary objectives
- Treatment line
 - Applied to primary objective 2 and 3

IMDC risk factors (each criterion accounts for +1 for the risk score):

1. Less than a year from time of initial RCC diagnosis to initiation of treatment for the metastatic RCC

2. Performance status* <80% (Karnofsky)
3. Hemoglobin* below normal (women < 117 g/l; men < 134 g/l)
4. Serum calcium* above normal (> 2.51 mmol/l)
5. Neutrophiles* above normal (> 6.3 x 10⁹/l)
6. Thrombocytes* above normal (> 350 x 10⁹/l)

** for performance status and laboratory values data of ± 3 months around the treatment initiation will be utilized due to possibly sparse data. If multiple records are available, the record closest to the treatment initiation will be utilized.*

Table 1. IMDC risk scores and categories based on two different approaches depending on the data coverage

	IMDC risk category	Total score of IMDC risk factors	Explanations/missing values
Option 1*	Favorable risk	0	no missing values allowed
	Intermediate risk	1-2	1) total score = 1; max 1 risk factor allowed to have missing value 2) total score = 2; no missing values allowed
	Poor risk	3 or more	max 3 risk factors allowed to have missing values
	Unknown risk**	-	when none of the above risk categories can be assigned
Option 2*	Appear favorable	0	all non-missing values for the risk factors indicate favorable risk max 3 risk factors allowed to have missing values
	At least intermediate	≥1	at least one risk factor criterion is met max 3 risk factors allowed to have missing values
	Poor	≥3	at least three risk factor criteria is met max 3 risk factors allowed to have missing values
	Unknown**	-	when none of the above risk categories can be assigned, i.e. more than 3 risk factors have missing value

** If small number of missing values is observed, the option 1 will be selected. If large number of missing values is observed and thus majority of patients were to belong to the “unknown” group of the option 1, the option 2 will be selected. The selection will be done after the data release and monitoring of data coverage.*

*** Patients with unknown risk category, will be analysed as own patient group.*

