7.3. Variables

Source for all variables is the data lake of HDSF.

Table 2. List of study variables. Abbreviations: PO=primary objective, SO=secondary objective.

Variable	Role/Relevant objective	Operational definition
ICD-10 diagnoses; RCC diagnoses	Patient inclusion/exclusion IMDC risk category	yes/no
ICD-10 diagnoses: co-diagnoses (e.g. renal insufficiency and hypertension)	PO1, SO1	yes/no; co-diagnoses before and after index
Date of birth	Patient inclusion PO1	Date; age defined at index based on birth date
Date of death	End of follow-up PO3	Date
Gender	PO1	Female/male
Home municipality	Patient inclusion End of follow-up	Home municipality at each healthcare contact
Weight	PO1	kg
Height	PO1	m
Body mass index (BMI)	PO1	derived from weight and height
Smoking status (if available in structured format)	PO1	yes/no
Outpatient visits (including emergency room visits)	Patient inclusion and index definition (visits to oncologist) SO2	Date, physician's specialty, type of arrival
Hospitalizations	SO2	Start and end dates
Procedures and operations (including nephrectomy)	PO1 SO1 SO2	Procedure code, date
Medical imaging	SO1 SO2	Imaging code, date
Medications; including - hospital medications - prescriptions	Patient inclusion/exclusion and index definition PO2 PO3 SO1 SO2	Dates, ATC-codes, active substance
Laboratory testing	IMDC risk category PO1	Dates, test id, result
Zubrod/ECOG performance status	IMDC risk category PO1	scale 0-5; converted to Karnofsky
PAD histology (if available in structured format)	PO1	
Staging of RCC, the tumor-node-metastasis (TNM) classification	Patient inclusion and index definition PO1	scale 1-4 (stages)

PFIZER CONFIDENTIAL

Table 3. List of medications for RCC treatment. ATC= Anatomical Therapeutic Chemical.

	Active substance	Brand name	ATC-code at the moment in use	ATC-code previously in use
Oral medications	axitinib	Inlyta	L01EK01	L01XE17
	everolimus	Afinitor	L01EG02	L01XE10
	cabozantinib	Cabometyx	L01EX07	L01XE26
	pazopanib	Votrient	L01EX03	L01XE11
	sorafenib	Nexavar	L01EX02	L01XE05
	sunitinib	Sutent	L01EX01	L01XE04
Intravenous medications	ipilimumab	Yervoy	L01XC11	
	nivolumab	Opdivo	L01XC17	

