7.7. Data analysis

Data will be analyzed using primarily descriptive measures, which include mean/median values for continuous variables and proportions for categorical variables. Costs will be estimated using data of visits, hospitalizations, procedures, etc. and utilizing publicly available price listings. For treatment outcomes, Kaplan-Meier estimates and/or corresponding time to event competing risk models will be utilized.

All analyses will be reported for the whole advanced/metastatic RCC patient population and stratified by the IMDC risk score. Additionally, treatment patterns and treatment outcomes will be reported by treatment lines.

Analyses are based on structured data, with the exception for potential text-mining of IMDC risk score or its components.

Due to the retrospective nature of the study, missing and/or incomplete data is expected in some of the medical records. Patients' records will not be excluded because of missing values, and missing data will not be imputed, i.e. the data will be analyzed as they are recorded in the electronic medical records. The proportion of missing values per variable will be reported.

Analyses will be performed using R, a language and environment for statistical computing, in Rstudio-server environment.

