7.7.1. Patient characteristics

[figure not shown]
Primary objective 1:

Demographical and clinical variables of RCC and mRCC patients will be summarized at index. Treated and non-treated mRCC patients will be analysed separately. For laboratory measures and performance status, the closest available measure +/- 90 days from index will be utilized. In case of a high rate of missing values, the time window can be extended to 6 months.

The demographical and clinical variables include but are not limited to:

- age at index
- sex
- history of renal insufficiency (any records until index)
 - ICD-10 code: N17-N19
- history of dialysis (any records until index)
 - procedure codes: TK800, TK829, TK810,
 - ICD-10 code: Z49

PFIZER CONFIDENTIAL

- history of kidney transplant (any records until index)
 - procedure codes: KAS10, KAS20
 - ICD-10 code: Z94.0
- history of nephrectomy (any records until index)
 - procedure codes: KAC*, KAD*, KAS40, KAS41
 - ICD-10 code: Z90.5
- performance status at index
 - Karnofsky (converted from Zubrod/ECOG)
- time from initial diagnosis of RCC to initiation of treatment for metastatic RCC
- various laboratory measures (e.g. hemoglobin, serum calcium, neutrophiles, thrombocytes, creatinine, albumin, eGFR)
- smoking status (if available in structured format)
- histology (if available in structured format)
- BMI (if available in structured format)

For categorical variables, the number (N) and the proportion (%) of patients in each class will be reported. For continuous normally distributed variables, mean and standard deviation (SD) will be reported. For continuous, non-normally distributed variables, median, the 1st quartile and the 3rd quartile will be reported.

The difference between strata will be tested using chi-squared/Fisher's exact test (categorical variables), t-test (continuous normally distributed variables) and Kruskal-Wallis test (continuous non-normally distributed variables).

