7.7.6. Changes in coding practices over time

Exploratory objective 1:

Assess changes in coding practices as a proportion of patients with data available respect to the diagnosis year of advanced/metastatic RCC. Variables of interest include but are not limited to

- structured IMDC risk score
- ICD-10 diagnosis for metastatic disease (C77*-C79*)

Other aspects of changes in coding practices may also be analyzed, if reasonable.

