7.9. Limitations of the research methods

All the data is recorded by the hospital during everyday practice and most of the data is stored in structured format. Therefore, rather high quality of the data is expected. However, as with all RWD, it is plausible to have erroneous entries. Also due to the retrospective nature of the study, missing and/or incomplete data is expected in some of the medical records. Patients' records will not be excluded because of missing values, and missing data will not be imputed, i.e. the data will be analyzed as they are recorded in the electronic medical records. The proportion of missing values per variable will be reported.

The treatment lines will be defined based on the medication data and therefore, misclassification of treatment lines is possible. However, the start and end dates of each main drug are expected to be recorded rather precisely, and the clinician PPD will be consulted when constructing the treatment lines. Thus, the majority of the treatment lines are expected to be defined correctly.

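### The background describes the IMDC calcium factor on corrected calcium, but the scoring rule uses serum calcium without saying whether it is corrected, so some patients may be put in the wrong risk group

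*Combined protocol and SAP*

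**What the plan says.** Section 5 (Rationale and background) lists the six IMDC predictors. The calcium one is "hypercalcaemia (corrected calcium concentration >upper limit of normal").

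Section 7.2.3 (Patient stratification) gives the operative list. Factor 4 is serum calcium "above normal (> 2.51 mmol/l") and adds 1 to the score. The asterisk on it refers to a note that sets only the ±3-month window around treatment initiation and the closest-record rule.

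Table 1 in the same section turns the score into categories. Option 1 limits missing values, for example for intermediate risk: "total score = 1; max 1 risk factor allowed to have missing value". Its footnote selects Option 1 when few values are missing, and Option 2 when so many are missing that most patients would be unknown under Option 1.

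Table 2 (section 7.3) defines laboratory data as "Dates, test id, result", with no derived calcium variable. Section 7.7.1 lists "various laboratory measures (e.g. hemoglobin, serum calcium, neutrophiles, thrombocytes, creatinine, albumin, eGFR") as patient characteristics, taken around index and not around treatment initiation. Section 7.9 (Limitations) does not mention the calcium measure.

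**The concern.** The protocol describes a published prognostic model in one way and scores it in another, under the same name and without comment. No section gives a correction formula, makes albumin an input to the score, or declares measured calcium to be a departure from the model.

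The category built from this score is the main stratification (section 7.1). It applies to all primary and secondary objectives (7.2.3) and enters the Cox models (7.7.3). If the recorded result is measured calcium, an analyst who follows 7.2.3 exactly will place some patients in a stratum that does not match the model in section 5, and a reader of the results could not tell.

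**Working it through.** The plan has no figure of its own to reproduce here. The check has three steps.

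**1. When is factor 4 misscored?** The documents give no correction formula, so I assume a linear one:

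corrected = measured + 0.02 × (40 − albumin in g/l), in mmol/l.

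- Measured 2.42, albumin 34: 2.42 + 0.02 × 6 = 2.54. The factor is met as section 5 describes it, but not under 7.2.3 applied to the measured value.
- Measured 2.42, albumin 38: 2.42 + 0.02 × 2 = 2.46. The score is the same either way.
- Measured 2.55, albumin 45: 2.55 − 0.02 × 5 = 2.45. The factor is met on the measured value only.

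Low albumin alone is therefore not enough; the correction has to carry calcium across 2.51. The measured value equivalent to a corrected 2.51 is 2.41 at albumin 35 and 2.61 at albumin 45. With slopes of 0.015 and 0.025 it is 2.435 and 2.385 at albumin 35.

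**2. When does a misscored factor change the category?** I applied the Table 1 rules with factor 4 switched from 0 to 1. Under Option 2, I read three or more factors as poor in preference to at least intermediate.

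| Rule | Other factors missing | Other-factor sums at which the group changes |
|---|---|---|
| Option 1 | 0 | 0 (favourable/intermediate), 2 (intermediate/poor) |
| Option 1 | 1 | 0 (unknown/intermediate), 1 (intermediate/unknown), 2 (unknown/poor) |
| Option 1 | 2 or 3 | 2 (unknown/poor) |
| Option 2 | 0 to 3 | 0 (appear favourable/at least intermediate), 2 (at least intermediate/poor) |

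**3. How many patients?** The documents give no calcium or albumin distribution, so every input here is an assumption:

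- Corrected calcium is normal with mean and SD 2.30/0.10, 2.35/0.10, 2.38/0.12 or 2.42/0.15. That puts 1.8, 5.5, 13.9 or 27.4% above 2.51.
- Albumin has mean 32, 35, 38, 40 or 42 g/l and SD 3, 4, 5 or 6, independent of corrected calcium.
- The other five factors (time under 1 year, performance status, haemoglobin, neutrophils, platelets) are independent, with prevalences .40/.15/.40/.15/.15, .50/.20/.50/.18/.22 or .55/.30/.55/.25/.30. The probability that they sum to 0 or 2 is then 0.496, 0.472 or 0.437.

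Share changing category with complete data = P(factor 4 misscored) × P(other five sum to 0 or 2).

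- Smallest: 0.0157 (calcium 2.30/0.10, albumin 35, SD 3) × 0.437 = 0.007.
- Largest: 0.220 (calcium 2.38/0.12, albumin 42, SD 6) × 0.496 = 0.109.
- One cell in between (calcium 2.38/0.12, albumin 38, SD 3, highest prevalences): 0.079 × 0.437 = 0.034. Against the 220 to 550 patients in section 7.5, that is about 7 to 19, before untreated patients are excluded.

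A slope of 0.025 in place of 0.02 gives 0.007 to about 0.13.

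**Direction.** With calcium 2.42/0.15, mean albumin 32 gives 19.0 to 21.4% under-scored and 0.0 to 1.2% over-scored. Mean albumin 42 gives 1.7 to 4.8% under-scored and 12.2 to 17.1% over-scored. The sign depends on an albumin level that the documents do not give.

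**The case against.** The strongest reply is that 7.2.3 does not say the calcium is uncorrected. It is silent, and a corrected value is still a serum calcium result. If the laboratory item is already corrected, nobody is misscored and only a label is missing. This stands. A reader might infer that the plan knowingly scores uncorrected calcium and that its strata are therefore wrong, but the documents support only the conditional claim.

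A second reply is that section 5 is background and 7.2.3 gives the analyst one clear rule. That is true of the rule, but it does not explain why a score presented as the same model uses a differently described input. The statement that "the data will be analyzed as they are recorded in the electronic medical records" does not settle it either, because it explains why missing data are not imputed and does not choose a calcium measure.

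Third, one might argue that sparse data make the problem much worse. With exactly one other factor missing under Option 1, factor 4 decides the group in 80 to 97% of such patients on the assumed prevalences, against 44 to 50% with complete data. But that is a share of a subgroup of unknown size, and several of the moves are only to or from unknown. The Table 1 footnote also sends data with many missing values to Option 2, where only sums of 0 and 2 matter. The documents do not support sparse data as a general amplifier.

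Finally, every input to the size calculation is assumed, the range spans about fifteenfold, and no effect on a median or hazard ratio has been shown. This also stands.

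**Conclusion.** The mismatch in wording between section 5 and section 7.2.3 is certain. Its consequence is conditional on the recorded result being measured calcium, which the documents leave open.

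If it is measured, the assumed scenarios misscore factor 4 in 1.6 to 22.0% of patients, so at least 78% are scored correctly in every scenario. With complete data, 0.7 to 10.9% change category. These are illustrations and not bounds; other inputs would move both ends. They apply to patients whose category is computed from the component factors.

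A reader might infer a bias in a known direction in the stratified outcomes. The documents do not support that, since the net direction is unknown. The point does not invalidate a mainly descriptive study, but it affects the main stratifier, is cheap to settle, and should be settled before the data are seen.

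**What to change.** Before data release, establish from the test id whether the calcium result is measured or corrected, and reconcile sections 5 and 7.2.3. If it is already corrected, say so in 7.2.3; nothing more is needed.

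If it is measured, define factor 4 in 7.2.3 as albumin-corrected calcium above the upper limit of normal and state the formula. Use the albumin record closest to the selected calcium record, within ±3 months of treatment initiation; the index-based albumin of section 7.7.1 is not a substitute. Where albumin is absent, use measured calcium against the same limit, count it as non-missing for Table 1, flag it, and report the number by stratum.

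As a sensitivity check, take the patients with paired albumin and score those same patients both ways. Report the reclassification table and the IMDC-stratified outcomes under each. Keeping the patients fixed isolates the effect of the definition.

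If measured calcium is intended, state this in 7.2.3 and 7.9 as a departure from the model in section 5, and report the same two-way comparison.

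The cost is one definition, one derived variable and one sensitivity run; albumin is already listed and laboratory results carry dates. The drawback is a mixed definition for patients without albumin. Treating factor 4 as missing for them would cost more under Option 1: with the other five factors known, those with a sum of 0 or 2 would become unknown, which is 44 to 50% of them on the assumed prevalences. Declaring measured calcium is the cheapest route, but the strata then still differ from the model that the protocol describes.

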7. RESEARCH METHODS

7.1. Study design

This is a retrospective registry-based cohort investigation, utilizing existing data generated during routine clinical practice and available in the Hospital District of Southwest Finland HDSF data lake. All adult patients (age ≥ 18 years) with RCC diagnosis (C64*; '*' indicates any number) will be identified from the data lake of HDSF.

The main purpose of this study is to characterize the patient population of advanced/metastatic RCC, and their treatment patterns and treatment outcomes using medical records retrieved from HDSF data lake. The main patient stratification will be the IMDC risk category (see 8.2.3 Patient stratification). Patients with unknown risk score will be analyzed as an own patient group.

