- Treatment initiation for mRCC (sunitinib, pazopanib, cabozantinib, ipilimumab, nivolumab)

When analyzing the treatment outcomes, index is defined as the date of the treatment initiation.

End of follow-up (whichever of the following occurs first):

- Death
- Moving outside of HDSF
 - Approximated using data of healthcare contacts; no contacts to specialty care of HDSF within 2 years (patient censored at the last recorded visit)
- End of study (31.12.2021)

Length of follow-up (in years): ('end of follow-up' – 'index' + 1)/365.25

Definitions for characteristics cohort

Index:

- For mRCC patients, same as for the mRCC cohort (i.e. approximated metastasis date)
- For RCC patients, the date of the first record of RCC diagnosis (ICD-10: C64)

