7.7.3. Treatment outcomes

Primary objective 3:

The treatment outcomes will be assessed using time-to-event analysis, namely Kaplan-Meier fit or other relevant competing risk models. For each outcome, the time will be defined as follows (Figure 3):

- overall survival:
 - time from index until death (event) or end of study (censoring event)
 - when analysing by treatment lines, start the time from initiation of each treatment line
- progression free survival (PFS, defined using time to next treatment (TTNT) proxy):
 - time from initiation of the current treatment line until the initiation of the next treatment line (event), death (competing risk/event), or end of study (censoring event)

The Kaplan-Meier fits will be visualized, and the median survival/PFS of the patients will be reported as well, if reached.

Additionally, corresponding Cox proportional-hazards model will be fitted, including clinical variables as covariates (including but not limited to age, sex, IMDC risk score, diagnosis year, and treatment line number). The hazard ratios, 95% confidence intervals and p-values corresponding to each covariate will be reported.

[figure not shown]

Figure 3. Graphical illustration of definitions of treatment outcomes. Abbreviations: LOT = line of treatment.

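### The IMDC category can rest on records made after treatment start even when a pre-start record exists, because the ± 3 month closest-record rule has no pre-start preference

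*Combined protocol and SAP*

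**What the plan says.** All references are to the combined protocol and SAP, with the section numbers used in its body text.

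- Section 7.1: "The main patient stratification will be the IMDC risk category". Section 7.2.3 applies it to all primary and secondary objectives.
- Section 7.2.3 gives its time point: "defined at the initiation of the first treatment for the metastatic RCC".
- The same section marks five of the six factors (performance status, haemoglobin, calcium, neutrophils, platelets) with a footnote: "for performance status and laboratory values data of ± 3 months around the treatment initiation will be utilized due to possibly sparse data". With several records, "the record closest to the treatment initiation will be utilized". The sixth factor, diagnosis to treatment in under a year, depends on dates only and is not exposed.
- Section 7.2: "When analyzing the treatment outcomes, index is defined as the date of the treatment initiation". Section 7.7.3 starts TTNT at the start of the current line, and by-line OS likewise.
- Section 7.7.3 lists the Cox covariates as "including but not limited to age, sex, IMDC risk score, diagnosis year, and treatment line number".

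The text does not prefer pre-start values, give a tie-break, count post-start values or plan a sensitivity analysis on timing. Section 7.9 (limitations) does not mention the matter. Section 7.7 promises the proportion missing per variable, which is a different quantity, and rules out imputation.

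**The concern.** A covariate labelled baseline should be known at time zero. Under the closest-record rule, a value from day +5 displaces one from day -6. If blood counts or performance status move soon after treatment starts, through treatment or disease course, part of that movement is recorded as baseline risk and then used to describe or adjust survival from that same date.

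The exposed analyses are mainly OS from first treatment and first-line TTNT. For later lines, most of the records used precede that line's time zero.

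A second mechanism is separate. A factor recorded only after the start requires the patient to live until that record, so whether a patient can be scored may depend on early death. As written, the report would not show how many patients either mechanism concerns.

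**Working it through.** **Plan's own figure.** There is none on this point. The only size figure (section 7.5) reproduces: 1,100 × 0.20 = 220 and 1,100 × 0.50 = 550 mRCC patients. The treated cohort's size is not stated, so no headcount is given below.

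**All inputs below are assumptions**, since the documents give no record timing.

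*1. How often a post-start value is used.* Let the nearest record before start be exponential with mean g days and the nearest after with mean h days; a = 1/g, b = 1/h; 90-day window. Pairs (g, h): (7,30), (14,14), (30,14), (30,30), (30,7). Either no patients or half have a day-0 record.

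- Post-start value chosen: b/(a+b) × [1 − exp(−90(a+b))]. For (30,7): 30/37 × 1.00 = 81%. For (7,30) with half on day 0: 0.5 × 7/37 = 9.5%. Range 9-81% per factor.
- Chosen value from days 29-90: b/(a+b) × [exp(−28(a+b)) − exp(−90(a+b))]. The largest is (30,30): 0.5 × (0.155 − 0.002) = 7.6%. Range 0.1-8%.
- Post-start value still needed under a pre-start-first rule: exp(−90a) × [1 − exp(−90b)], at most exp(−3) × 1.00 = 5.0%. Range 0-5%.

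A different model (independent Poisson record streams, before:after rates 4:1 to 1:4) gives 20-80% post-start under the closest-record rule and 1-36% under pre-start-first. Both models agree that the rule can make post-start values common and that the change reduces them; neither estimates the true share.

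*2. Effect on category through one factor.* Platelets lognormal (log-SD 0.35), 20% or 30% above 350 before start, falling linearly by 10% or 30% by day 28. The other five factors are complete and independent, with prevalences 0.4/0.2/0.4/0.1/0.15 or 0.6/0.3/0.6/0.1/0.25 in the plan's order. Losing this factor changes the category only if the other five sum to 0 (intermediate to favourable) or 2 (poor to intermediate). Simulating 1,000,000 patients per scenario gives about 0.1-3% of patients changing category under the closest-record rule and at most about 0.4% under pre-start-first.

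*3. Survival-dependent scorability.* If 10-30% have one factor recorded only after start, on a day d uniform over 1-90, and 90-day mortality is 5-20%, the share f × mean[1 − exp(−λd)] losing it by dying first is 0.3-3.1%. Under Option 1, with the other five factors complete, 43-51% of these become 'unknown' (observed score 0 or 2), or 0.1-1.6% of patients. Under Option 2 none do if the other five are complete, because 'unknown' there means "i.e. more than 3 risk factors have missing value".

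*4. Several factors lost together, Option 1.* With two missing, only an observed score of 3 or more can be classified. The most favourable case leaves prevalences 0.6, 0.3, 0.6, 0.3: P(3 or more of 4) = 0.0324 + 0.0432 + 0.1512 = 0.227, so 77% are 'unknown'. With three missing, all three remaining factors must be present: 0.6 × 0.3 × 0.6 = 0.108 leaves 89% 'unknown', and 0.4 × 0.1 × 0.15 = 0.006 leaves 99%. Overall, about 77-99% of patients who lose two or three factors.

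*5. Staleness caused by the change.* The probability that the pre-start record is 29-90 days old and a closer post-start one is passed over is [exp(−28a) − exp(−90a)] − a/(a+b) × [exp(−28(a+b)) − exp(−90(a+b))]. For (30,7): 0.343 − 0.001 = 34%. For (7,30) with half on day 0: 0.6%. Range 0.6-34% per factor.

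**The case against.** The window is disclosed and has a reason: sparse data. The closest record usually resembles the patient's state at the start; most post-start values would be early ones, and the category change illustrated is small. The study is mainly descriptive, and no effect on a survival curve or hazard ratio has been shown. A pre-start-first rule trades slight contamination for older data: in the (30,7) scenario 34% of patients get a record more than 28 days old, and in 22% the record passed over was within 7 days of start. Section 7.7.2 may date a line by prescription, and six of the eight drugs in Table 3 are oral, so a record just after that date may still precede the first dose.

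Much of this stands and limits the weight of the point. Two things do not follow. Sparse data justifies using a post-start record when nothing earlier exists; it does not justify preferring one when a pre-start record is available. And the general coverage and plausibility checks in section 7.8 would not count post-start values. Sections 7.7 and 7.7.6 also mention text-mined or structured IMDC scores, but section 7.2.3 is the operational definition. Figure 1, on study time windows, was not visible in the text available.

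A reader might infer that every IMDC-stratified result is compromised, since the category applies to all primary and secondary objectives. The documents do not support that: the exposure is mainly OS from first treatment and first-line TTNT.

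**Conclusion.** The point holds. The text lets post-start values displace available pre-start ones in a category defined at treatment start, and nothing in the plan flags, counts or tests this. It is a worthwhile, inexpensive improvement.

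Its size is not known. The only category effect illustrated is about 0.1-3% of patients through platelets alone, resting on assumed record timing, platelet fall and prevalences; it does not cover the other four exposed factors. The direction of bias is undetermined.

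Two stronger readings should be resisted. The 9-81% range is not an estimate of how many patients are misclassified: it is a per-factor share of post-start values under assumed timing, mostly early ones. Nor does losing a factor lead to 'unknown' only at score 0 or 2 under Option 1, and never under Option 2. That holds only when the other five factors are complete. A patient at score 1 with one factor already missing becomes 'unknown' under Option 1 on losing another, and a patient already missing three does so under Option 2.

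**What to change.** 1. In section 7.2.3, take the closest record on or before treatment start within the existing 3-month window, and a post-start record within 3 months only if there is none.
2. Flag post-start values and report their number per factor and by day band (1-7, 8-28, 29-90).
3. As a sensitivity analysis, repeat the IMDC-stratified and Cox analyses of OS and first-line TTNT with post-start values set to missing and Table 1 reapplied, showing the size of 'unknown'. If Option 1 is the main choice, show this run under Option 2 as well, because Option 1 may leave little to compare when several factors are lost together. Only this run, not the main rule, bears on survival-dependent scorability.
4. Also report the result under the plan's current closest-record rule, so that the effect of older values can be seen.

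The cost is one changed selection rule, one flag, one count table and the additional runs, on data already listed in Table 2. Main-analysis coverage is unchanged because the fallback stays. The downsides are the older records quantified above and, where the start is dated by prescription, passing over some records that may precede the first dose; the day 1-7 band and item 4 make both visible.
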